8.2.1. Hypothesis Testing

The hypothesis to be tested for the estimand for the primary effectiveness endpoint is:

$$H_0: p_A - p_B \leq d_0 \quad \text{versus} \quad H_1: p_A - p_B > d_0$$

This document is confidential.

where, p_A is the response rate for Princess® FILLER Lidocaine, p_B is the response rate for Juvéderm® Ultra XC, and d_0 is the non-inferiority margin set at -10%.

A negative value for the difference $p_A - p_B$ indicates that the response rate of Princess® FILLER Lidocaine is lower than the response rate for Juvéderm® Ultra XC.

The hypothesis testing of non-inferiority for paired proportions will be tested using a 1-sided, McNemar type test at an alpha of 0.025 with a delta of 0.10 (10%). Princess® FILLER Lidocaine will be considered non-inferior to Juvéderm® Ultra XC if the lower limit of the 2-sided 95% confidence interval (equivalent to the 1-sided 97.5% CI) for the difference between the proportions is greater than -10%.

McNemar type test using a GENMOD procedure and taking into account of paired data will be used for testing the non-inferiority of the rate difference in paired proportions considering non-inferiority margin (-10%).

SAS code for comparison of paired proportions could refer:

```
ods output parameterestimates=paramest;
proc genmod data=indiv;
  class id treatment;
  model response (event='1')=treatment/dist=binomial link=identity;
  repeated subject=id;
  lsmeans treatment/diff cl;
  lsmestimate treatment/cl lower testvalue=-0.1 alpha=0.025;
run;
```

Above analysis and confirmatory testing will be repeated on PPS.

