8.4. Sensitivity Analysis

Single imputation:

Best-case analysis will be conducted as sensitivity analysis for the primary outcome measure, as well as the key secondary outcome measures on the FAS and PPS. Missing values will be imputed using single imputation strategy for Princess® FILLER Lidocaine as a response, and for Juvéderm® Ultra XC as a non-response. This endpoint will be analyzed as described in [section 8.2.1](#).

Similarly, worst-case analysis will be conducted as sensitivity analysis for the primary outcome measure, as well as the key secondary outcome measures on the FAS and PPS. Missing values will be imputed using single imputation strategy for Princess® FILLER Lidocaine as a non-response, and for Juvéderm® Ultra XC as a response. This endpoint will be analyzed as described in [section 8.2.1](#).

Multiple imputation:

A sensitivity analysis will be conducted for the estimand of the primary outcome measure, as well as the key secondary outcome measures (NFL-SRS assessments) using a method of multiple imputation on the FAS and PPS, under the missing-at-random (MAR) assumption for all missing values at Week 24. If baseline is missing one side of the face, then impute from the other side of the face, but if baseline is missing for both sides of the face then impute using multiple imputation with the Markov Chain Monte Carlo (MCMC) method. Additionally, a tipping point analysis will be performed for the estimand of the primary outcome measure, as well as the key secondary outcome measures on the FAS, by performing a series of multiple imputations with adding an increasing shift value to the original NLF-SRS scale (discrete) of imputed subjects prior to performing the treatment comparison to investigate the impact of the deviation from MAR assumption. The number of completed datasets for each multiple imputation approach will be 100. The multiple imputations will be performed via SAS PROC MI procedure.

Impute: The missing values on the NLF-SRS scale (discrete) will be multiple imputed (using MAR assumptions) for each subject (with missing NLF-SRS post-baseline) with a set of 100 plausible values, thus 100 completed datasets will be produced. The multiple imputations will be done via SAS PROC MI. As per MAR assumption, all available observations with similar baseline characteristics from same treatment group are used to derive the imputation model.

This document is confidential.

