The following statements use the MI procedure to impute missing values under the MAR assumption:

Achieve monotone missing data pattern for all visits:

```
proc mi data=dain seed=12345 nimpute=100 round=1 minimum=0 maximum=4
out=mono;
  class treatment;
  var treatment sex age base week12 week24;
  mcmc impute=monotone;
run;
```

Impute under the MAR assumption for all visits with monotone missing data pattern:

```
proc mi data=mono seed=12345 nimpute=1 round=1 minimum=0 maximum=4
out=outmi;
  by _Imputation_;
  class treatment;
  var treatment sex age base week12 week24;
  monotone reg;
run;
```

Categorization of Response: The category of response/non-response for each subject will be derived based on the imputed NLF-SRS scale for the missings in each of the 100 completed datasets.

Analyze: The analysis method as described in [section 8.2.1](#) will run in each of the 100 completed datasets using binary response data.

Combine: The analysis results / estimates resulting from 100 completed datasets will be combined using Rubin's combination rules (Rubin D.B., 2004) with SAS MIANALYZE procedure.

```
ods output parameterestimates=paramest;
proc mianalyze data=paramest;
  modeleffects estimate;
  STDERR stderr;
run;
```

Tipping point is a series of multiple imputations whereby a shift (here a positive shift) will be applied on the original NLF-SRS scale (discrete) of imputed subjects to the treatment group Princess® FILLER Lidocaine, which results then in the decrease of the number of responses in this group, and thus decreases the likelihood of non-inferiority against the control treatment Juvéderm® Ultra XC. This shift is only applied to subjects where missing values have been multiple imputed.

The positive shift of 1, 2, 3, 4 will be performed in each step, until the point is reached where the statistically significant non-inferiority switches to statistically non-significant: This respective shift where this happens is the tipping point.

A sample of SAS code for sensitivity analysis using the tipping-point method could refer to:

```
/*-----*/
/*--- Performs multiple imputation analysis           ---*/
/*--- for specified shift parameters:                 ---*/
/*--- data= input data set                           ---*/
```

This document is confidential.

```
/*--- smin= min shift parameter ---*/
/*--- smax= max shift parameter ---*/
/*--- sinc= increment of the shift parameter ---*/
/*--- outparams= output reg parameters ---*/
/*-----*/

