%macro miparams(data=, smin=, smax=, sinc=, outparams=);
ods select none;

data &outparams;
  set _null_;
run;

/*----- # of shift values -----*/

%let ncase= %sysevalf( (&smax-&smin)/&sinc, ceil);

/*---- Multiple imputation analysis for each shift ----*/
%do j=0 %to &ncase;
  %let sj= %sysevalf( &smin + &j * &sinc);

/*---- Generates 100 imputed data sets ----*/

proc mi data=&data seed=12345 nimpute=100 round=1 minimum=0 maximum=4
out=mono;
  class treatment;
  var treatment sex age base week12 week24;
  mcmc impute=monotone;
run;

proc mi data=mono seed=12345 nimpute=1 round=1 minimum=0 maximum=4 out=outmi;
  by _Imputation;
  class treatment;
  var treatment sex age base week12 week24;
  monotone reg;
  mmar adjust( week24 / shift=&sj adjustobs=(treatment='1') );
run;

/*---- Categorization of response in imputed data sets ----*/

data outmi;
  set outmi;
  chg= week24 - base;
  if chg<0 then response=1;
  else response=0;
run;

/*----- Perform genmod test -----*/

ods output parameterestimates=paramest;
proc genmod data=outmi;
```

This document is confidential.

```
    by _Imputation_;
    class id treatment;
    model response (event='1')=treatment/dist=binomial link=identity;
    repeated subject=id;
    lsmeans treatment/diff cl;
    lsmestimate treatment/cl lower testvalue=-0.1 alpha=0.025;
run;

/*----- Combine genmod results -----*/

ods output parameterestimates=miparams;
proc mianalyze data=paramest;
    modeleffects estimate;
    STDERR stderr;
run;

data miparams;
    set miparams;
    Shift= &sj;
    keep Shift Probt;
run;

/*----- Output multiple imputation results -----*/
data &outparams;
    set &outparams miparams;
run;

%end;

ods select all;
%mend miparams;
```

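### The sample SAS code in SAP 8.4 pools intercept and treatment rows together, and the tipping-point macro drops the -10% margin, so it cannot show the shift at which non-inferiority is lost

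*SAP*

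**What the plan says.** SAP 8.2.1 sets the decision rule: Princess is non-inferior if the "lower limit of the 2-sided 95% confidence interval (equivalent to the 1-sided 97.5% CI) for the difference between the proportions" lies above -10%.

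The prose of SAP 8.4 carries that rule into the sensitivity analyses. The 8.2.1 analysis is run in each of 100 completed data sets and the results are combined by Rubin's rules. For the tipping point, imputed Princess scores are shifted upwards by 1, 2, 3 and 4 grades "until the point is reached where the statistically significant non-inferiority switches to statistically non-significant".

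SAP 8.4 also prints code, in two places.

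- **Combine block for multiple imputation.** It reads "proc mianalyze data=paramest" and "modeleffects estimate", with the standard-error column beside it.
- **Tipping-point macro**, introduced with "A sample of SAS code for sensitivity analysis using the tipping-point method could refer to". GENMOD runs by imputation with "lsmestimate treatment/cl lower testvalue=-0.1 alpha=0.025", but the only GENMOD table saved is the parameter-estimates table. The same two pooling statements follow, and the last data step has "keep Shift Probt".

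The SAP's Index of Tables plans multiple-imputation tables (FAS and PPS) and a tipping-point table (FAS) for the primary and both key secondary endpoints.

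**The concern.** The code and the prose describe different calculations, in two respects.

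1. **Row selection (both blocks).** The model has an intercept and a class effect for treatment. Pooling the whole table, with no filter or grouping on the parameter, treats those rows as repeated estimates of one quantity. The pooled figure is not a treatment difference.
2. **Margin (macro only).** The value -0.1 is used only in the LSMESTIMATE statement, whose result is not saved. No null value reaches the pooling step. Because only the shift and the p-value are kept, no pooled lower limit survives to compare with -10%.

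A tipping-point table built this way would give a plausible-looking p-value for each shift, yet would not show where non-inferiority is lost. That table is needed most when the worst-case analysis fails and the reader wants to know how far from missing-at-random the conclusion survives.

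**Working it through.** **Inputs.** Response rates 87% (Princess) and 88% (Juvéderm), independent folds (SAP 2.7); 270 randomized (SAP 2.6); margin -10%, one-sided 0.025 (SAP 8.2.1); 100 imputations (SAP 8.4).

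**The plan's own figures first.** One-fold response: 0.87×0.12 + 0.13×0.88 = 0.1044 + 0.1144 = 0.2188, the SAP's 21.9%. Both folds: 0.87×0.88 = 0.7656, printed as 76.5%. Simulating the stated design (222 subjects, one-sided 95% Newcombe limit, 400,000 runs) gives 88.4% to 88.6% power against the stated 90%. The inputs are therefore usable; the point itself does not depend on the sample size.

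**Correct pooled test, no shift.** d = 0.1044 - 0.1144 = -0.010. SE = √[(0.2188 - 0.0001)/270] = 0.0285. Lower limit = -0.010 - 1.96×0.0285 = -6.6%. z against -0.10 = 0.090/0.0285 = 3.16, one-sided p = 0.0008. Between-imputation noise is ignored here and in the table below.

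**Code as written, no shift.** The layout of the saved table is an assumption: 2 rows (intercept, effect), 3 (plus a reference row of 0) or 4 (plus a scale row of 1), with either device as reference. A null value of zero in the pooling step is also assumed, as none is given. With 3 rows and Juvéderm as reference:

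- pooled estimate = (0.88 - 0.01 + 0)/3 = 0.29
- between-row variance = [(0.59² + 0.30² + 0.29²)/3]×300/299 = 0.1747
- within variance = (0.88×0.12/270 + 0.0285²)/3 = 0.0004
- total SE = √(0.0004 + 0.1747×301/300) = 0.419; t = 0.29/0.419 = 0.69; p = 0.49

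Across all six layouts the estimate runs from 0.29 to 0.47 and p from 0.31 to 0.49.

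**As the imputed Princess response falls.** Let a share m be missing on both sides, with imputed Princess response a = 0.87(1 - f) and Juvéderm 0.88. Then p10 = (1-m)×0.87×0.12 + m×a×0.12 and p01 = (1-m)×0.13×0.88 + m×(1-a)×0.88. Worked case, m = 10%, f = 60%: a = 0.348; p10 = 0.0981; p01 = 0.1603; d = -0.0622; SE = √[(0.2585 - 0.0039)/270] = 0.0307. Against 0, z = -2.03 and p = 0.043; against -0.10, z = 0.0378/0.0307 = 1.23 and one-sided p = 0.11.

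| Missing (assumed) | Cut f | One-sided p against -10% (correct) | p against 0, treatment row only | p as written (six layouts) |
|---|---|---|---|---|
| 5% | 70% | 0.023 | 0.18 | 0.28–0.51 |
| 5% | 80% | 0.033 | 0.14 | 0.27–0.52 |
| 5% | 100% | 0.063 | 0.078 | 0.26–0.52 |
| 10% | 30% | 0.016 | 0.22 | 0.28–0.51 |
| 10% | 40% | 0.033 | 0.14 | 0.27–0.52 |
| 10% | 60% | 0.11 | 0.043 | 0.25–0.53 |
| 10% | 100% | 0.46 | 0.0024 | 0.20–0.56 |

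As written, p stays non-significant whether non-inferiority is held or lost. With row selection alone repaired, p against zero is non-significant at first and can turn significant only after non-inferiority has gone (10% missing: lost between cuts of 30% and 40%, p against zero below 0.05 by 60%). That is the reverse of the prose criterion.

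**On the SAP's own shift steps.** These are illustrative: one simulated data set per missing rate, baselines split between grades 2 and 3, 30% of responders improving two grades. At 10% missing, shifts 0, 1, 2 give 0.0002, 0.083, 0.31 for the correct test, 0.88, 0.096, 0.009 against zero, and 0.48, 0.52, 0.55 as written. The true tipping point is shift 1, and the as-written p does not register it. At 5% missing that data set keeps non-inferiority at every shift (p 0.001 to 0.012).

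**The case against.** The pre-specified rule in the prose is correct, and a programmer who follows 8.2.1 and the text of 8.4 would obtain the right table. The macro is offered only as a sample. As printed it has a BY variable without its closing underscore and an odd `mmar` statement (either may come from PDF conversion), so it would need reworking before it ran. SAP 14 plans quality control of program logic, and SAP 18 cites a shells document that was not available here. All of this stands and is why the point is minor. It does not remove the defect: this is the only implementation the SAP prints, and the Combine block carries no sample label.

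The worst-case analysis, with imputation "for Princess® FILLER Lidocaine as a non-response, and for Juvéderm® Ultra XC as a response", is analyzed under 8.2.1 with the right margin and bounds the result. At the planning rates its lower limit is -9.8% with 3% missing, -12.0% with 5% and -17.3% with 10%. It bounds the answer but does not locate the tipping point.

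Four stronger readings are tempting and are not supported:

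- **That the multiple-imputation block also loses the margin.** It discards nothing. Once the treatment row is isolated, its pooled lower limit can be set against -10% directly.
- **That the primary test is affected.** Section 8.2.1 has no pooling step, and its prose states the correct rule.
- **That with correlated folds the repaired-row p would fire while non-inferiority still held.** The SAP gives no fold correlation, and this needs a paired standard error. If the saved table is the independence-model one, as the four-row layout implies, p with 5% missing and all imputed Princess values non-response is 0.078 whatever the correlation.
- **That the worst case is expected to fail.** Protocol 9.3 expects about 5% lost to follow-up overall; that is not a Week 24 missing rate. Here 5% is only an assumed value.

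**Conclusion.** The code is wrong as written, with minor consequence. Both blocks of 8.4 pool unlike rows, and the macro in addition cannot apply the -10% margin or show the shift at which non-inferiority is lost. At the planning rates the contrast is a one-sided p of 0.0008 (correct) against a p of about 0.3 to 0.5 (as written).

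The absence of row selection, the unsaved margin result and the dropped limits can be read directly from the printed statements. The as-written p-values rest on an assumed table layout and null value, which is why they are given as a range. The percentage cuts and the 5% and 10% missing rates are assumptions, not SAP steps. Only the multiple-imputation and tipping-point analyses are affected; the primary, best-case, worst-case and complete-case analyses are not.

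**What to change.** - **Both blocks:** save the Princess-minus-Juvéderm risk difference and its paired (GEE) standard error from each imputation, with explicit contrast coefficients, and pool only that row.
- **Multiple-imputation block:** compare the pooled lower limit of the two-sided 95% interval with -10%.
- **Macro:** test the pooled difference against -0.10 at one-sided 0.025 (for example with THETA0=-0.1), or keep the pooled lower limit for each shift.
- **Text:** add one sentence naming that test or limit as the statistic that defines the tipping point.

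The cost is a few lines of sample code and one sentence. No new data are needed and the primary test does not change.

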8.5. Supportive Analysis

Complete-case analysis which includes subjects without any missing data will be conducted as supportive analysis for the primary outcome measure, as well as the key secondary outcome measures on the FAS and PPS. This endpoint will be analyzed as described in [section 8.2.1](#).

8.6. Other Secondary Effectiveness Endpoints and Analyses

8.6.1. GAIS Response Rate - Blinded Independent Evaluating Investigator

Aesthetic response rate based on blinded independent evaluating investigator assessment at Week 24 relative to Baseline using the GAIS. This endpoint will be analyzed descriptively presenting the response rate and one-sided 95% CIs using McNemar type test given in [section 8.2.1](#).

8.6.2. GAIS Response Rate - Subject Assessment

Aesthetic response rate based on subject assessment at Week 24 relative to Baseline using the GAIS. This endpoint will be analyzed descriptively presenting the response rate and one-sided 95% CIs using McNemar type test given in [section 8.2.1](#).

This document is confidential.

8.7. Additional Effectiveness Endpoints and Analyses

8.7.1. NLF-SRS Response Rate - Blinded Independent Evaluating Investigator

NLF-SRS response rate based on independent blinded evaluating investigator live assessments of NLF severity at Week 12, 36, 48 and the post repeat-treatment hold follow-up visit (Visit 7c) compared to Baseline using the NLF-SRS. This endpoint will be analyzed descriptively presenting the response rate and one-sided 95% CIs using McNemar type test given in [section 8.2.1](#).

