On Week 36 and/or Week 48 after initial treatment, an evaluation for repeat-treatment will take place; subjects will be offered an optional repeat-treatment (Visit 6 or 7), if in the opinion of the treating investigator, they have returned to sufficient severity of NLFs that would have qualified them for enrollment into the clinical investigation initially. The subjects do NOT have to return to their Baseline severity to be permitted to receive a repeattreatment. At Week 36, an evaluation for repeat-treatment will take place; subjects qualifying for a repeat-treatment will receive it during the same visit (Visit 6) and will come back for a safety follow-up visit four and twelve weeks later (Week 40/Visit 8a and Week 48/Visit 9a). For these subjects, Visit 9a will be their end of study visit. Subjects which are not qualifying for a repeattreatment at Week 36 will be evaluated again at Week 48 (Visit 7); qualified subjects will then receive a repeat-treatment during Visit 7 and will be followed-up for safety four and twelve weeks later (Week 52/Visit 8b and Week 60/Visit 9b). For these subjects, Visit 9b will be their end of study visit. Subjects, who do not qualify for any retreatment, will have their end of study visit at Visit 7. The repeat-treatment will be performed with Princess® FILLER Lidocaine on both NLFs.

Follow-up visits for effectiveness will be performed at Week 2, 12, 24, 36 and/or 48 after initial treatment. Follow-up visits for safety will be performed at Week 2, 4, 6 (only if touch-up treatment occurred at Week 2), 12, 24, 36/48 and 48/60 after initial treatment. In addition, subjects will be contacted by phone on

Day 3 (±24 hours) after initial, touch-up and repeat-treatments for a safety check-up. Also at the end of each treatment session, subjects will receive a diary to record the injection site reactions, as well as the incidence of serious adverse events associated with unintended intravascular injection over the following (four weeks after initial-, touch-up- and repeat-treatments.

Subject satisfaction with the outcome of the treatment will be assessed with GAIS and the patient-reported outcome questionnaires measuring experience and outcomes of aesthetic facial procedures (FACE-Q) questionnaires.

Pain assessment will be performed after initial and repeattreatment (15 min after last injection and at 15 min-intervals for 60 min post-treatment).

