2.5. Brief Description

This is a randomized, subject- and evaluating investigator-blinded, controlled, multicenter, split-face comparison clinical investigation of Princess® FILLER Lidocaine compared to Juvéderm® Ultra XC in the treatment of moderate to severe NLFs.

Eligible subjects will be randomized at Baseline (Visit 2/Day 0) in a 1:1 ratio to Group A or Group B and will receive an injection of Princess® FILLER Lidocaine and an injection of Juvéderm® Ultra XC as follows:

Group A:

- Princess® FILLER Lidocaine on left NLF
- Juvéderm® Ultra XC on right NLF

Group B:

- Juvéderm® Ultra XC on left NLF
- Princess® FILLER Lidocaine on right NLF

The left NLF will be treated first and the right NLF thereafter.

The initial treatment will be administered at Baseline (Visit 2/Day 0) after randomization.

A touch-up treatment may be done at Visit 3a (Week 2) if an optimal aesthetic correction has not been achieved after initial treatment, as evaluated by the treating investigator. A touch-up treatment will be performed using the same type of device as initially applied.

A repeat-treatment may be done at Visit 6 (Week 36) or Visit 7 (Week 48) or Visit 7c (post repeat-treatment hold follow-up visit), if in the opinion of the treating investigator, the subject has returned to sufficient severity of NLFs that would have qualified them for enrollment into the clinical investigation initially. A repeat-treatment will be performed with Princess® FILLER Lidocaine on both NLFs.

Repeat-treatment:

Subjects who received repeat-treatment at Visit 6 (Week 36) or Visit 7 (Week 48) or Visit 7c (post repeat-treatment hold follow-up visit) will be included in the repeat-treatment subgroup, and the demographic, other baseline characteristics, medication, and applicable safety data will be analyzed by Group A, Group B, and repeat-treatment subgroup.

Subjects who received a repeat-treatment at Visit 6 (Week 36) will come back for safety follow-up visits at Visit 8a (Week 40) and at Visit 9a (Week 48). For these subjects, Visit 9a will be their end of study visit. Subjects who received a repeat-treatment at Visit 7 (Week 48) will come back for safety follow-up visits at Visit 8b (Week 52) and at Visit 9b (Week 60). For these subjects, Visit 9b will be their end of study

This document is confidential.

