2.6.3. Inclusion Criteria - Repeat-treatment

Subjects who meet **ALL** the following criteria are eligible for a repeat-treatment:

1. In the opinion of the treating investigator, the subject has returned to sufficient severity of both NLFs that would have qualified him for enrollment into the clinical investigation initially (note that the subject does not have to return to his Baseline severity to be permitted to receive a repeat treatment)
2. Subjects with NLFs with severity scores of 2 or 3 on the 5 point NLF-SRS for both NLFs as judged by the treating investigator in conjunction with the independent blinded evaluating investigator (note that it is not necessary for the treating and evaluating investigator to agree on the same rating)
3. Females of childbearing age must have a negative urine pregnancy test at the repeat-treatment visit and must agree to continue to use an adequate method of contraception for the duration of the clinical investigation
4. Healthy skin in the nasolabial area and free of diseases that could interfere in cutaneous aging evaluation and/or injection

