6.3. Missing Data

For safety analysis missing data will not be estimated and/or imputed in any way. All subjects who withdraw prematurely from the study will be documented and the reason for withdrawal will be reported in the Clinical investigation report. All available data from subjects who withdraw will be listed and all available planned data will be included in the summaries according to analysis data sets.

In case of an AE/ ADE with partial/ missing start/ stop dates, the rules outlined in Section 9.3 will be applied.

Subjects with missing NLF-SRS grades at Baseline and/or at Week 24 will be considered as non-responders for the primary analysis. Since it is very unlikely that the assessment of only one NLF will be missing, presumably either no or both assessments will be available for one subject at a certain time point. Therefore, this imputation method will probably decrease the response rate in both treatment groups simultaneously. Due to the fact that the sample size calculation was based on rather high response rates (88% for Juvéderm® Ultra XC and 87% for Princess® FILLER Lidocaine), lower response rates will make it more difficult to demonstrate non-inferiority of Princess® FILLER Lidocaine and thus this approach is considered to be conservative. In addition to this approach, a complete case analysis (using the available data without any imputation), a best-case analysis (missing values for Princess® FILLER Lidocaine will be considered as a response, missing values for Juvéderm® Ultra XC will be considered as a non-response), a worst-case analysis (missing values for Princess® FILLER Lidocaine will be considered as a non-response, missing values for Juvéderm® Ultra XC will be considered as a response), and a tipping point analysis will be conducted as sensitivity analyses.

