8.1.9. Response Rate for NLF-SRS

The response rate for week X in treatment group A is defined as follows:

Response rate

$$= \frac{\text{Number of Responders at Week X with treatment A}}{\text{Number of Responders at Week X with treatment A} + \text{Number of Non-Responders at Week X with treatment A}}$$

The change from Baseline in NLF-SRS at Week X is calculated as follows (separately for the treatment groups):

$$= NLF - SRS_{\text{Week X}} - NLF - SRS_{\text{Baseline}}$$

'Responder' is defined as a subject with at least one grade improvement in NLF-SRS at Week X compare to Baseline.

Each subject's 'Response' for NLF-SRS will be assessed for both treatment groups, Princess® FILLER Lidocaine and Juvéderm® Ultra XC, in this split-face design.

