13.2.5.2. Table Conventions

- Units will be included where available
- If the categories of a parameter are ordered, then all categories between the maximum and minimum category are presented in the table, even if n=0 for all treatment groups in a given category that is between the minimum and maximum level for that parameter. For example, the frequency distribution for symptom severity would appear as:

Severity Rating	N
severe	0
moderate	8
mild	3

Where percentages are presented in these tables, zero percentages will not be presented and so counts of 0 will be presented as 0 and not as 0 (0%).

- If the categories are not ordered (e.g., Medical History, Reasons for Discontinuation from the Study, etc.), then only those categories for which there is at least 1 subject represented in 1 or more groups are included.
- An Unknown or Missing category are added to each parameter for which information is not available for 1 or more subjects.
- Unless otherwise specified, the estimated mean and median for a set of values are printed out to 1 more significant digit than the original values, and standard deviations are printed out to 2 more significant digits than the original values. The minimum and maximum should report the same significant digits as the original values. For example, for systolic blood pressure:

N	XX
Mean	XXX.X
Std Dev	X.XX
Median	XXX.X
Minimum	XXX
Maximum	XXX

- P-values are output in the format: "0.xxx", where xxx is the value rounded to 3 decimal places. Every p-value less than 0.001 will be presented as <0.001. If the p-value are less than 0.0001, then present as <0.0001. If the p-value is returned as >0.999, then present as >0.999
- Percentage values are printed to one decimal place, in parentheses with no spaces, one space after the count (e.g., 7 (12.8%), 13 (5.4%)). Pre-determine how to display values that round down to 0.0. A common convention is to display as '<0.1', or as appropriate with additional decimal places. Unless otherwise noted, for all percentages, the number of subjects in the

This document is confidential.

analysis set for the treatment group who have an observation will be the denominator. Percentages after zero counts should not be displayed and percentages equating to 100% are presented as 100%, without decimal places.

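### The Week 48 response rates rest only on subjects not retreated at Week 36, which biases them upward or at best leaves them unbiased; at Visit 7c the direction is undetermined

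*SAP*

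**What the plan says.** **Endpoints.** SAP 8.7.1 takes the blinded evaluator's NLF-SRS response rate "at Week 12, 36, 48 and the post repeat-treatment hold follow-up visit (Visit 7c) compared to Baseline". It adds: "This endpoint will be analyzed descriptively presenting the response rate and one-sided 95% CIs". SAP 8.7.2 to 8.7.5 repeat this for the photographic reviewers, the treating investigator and both GAIS ratings.

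**Who is seen at Week 48.** The Protocol synopsis (Design) says: "Subjects which are not qualifying for a repeattreatment at Week 36 will be evaluated again at Week 48 (Visit 7". For those retreated at Week 36, SAP 2.5 says: "Subjects who received a repeat-treatment at Visit 6 (Week 36) will come back for safety follow-up visits at Visit 8a (Week 40", followed by Visit 9a at Week 48. The visit lists in Protocol 10.11.12 and 10.11.13 contain no NLF-SRS, GAIS or photography at Visits 8a and 9a.

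**Who is retreated.** The criterion in SAP 2.6.3 and Protocol 9.2.1 is that "the subject has returned to sufficient severity of both NLFs that would have qualified him for enrollment into the clinical investigation initially", with a score of 2 or 3 in both folds. A return to the subject's own baseline grade is not required, and the synopsis calls repeat-treatment optional.

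**Denominator and missing data.** SAP 8.1.9 divides "Number of Responders at Week X with treatment A" by responders plus non-responders at that week. SAP 13.2.5.2 sets the default, unless noted otherwise: "analysis set for the treatment group who have an observation will be the denominator". Imputation is stated for the primary time point only: "Subjects with missing NLF-SRS grades at Baseline and/or at Week 24 will be considered as non-responders for the primary analysis". SAP 5.1 to 5.3 extend it to the key secondary endpoints, also at Week 24. Repeat-treatment is not listed as an intercurrent event.

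**Visit 7c.** It was added for subjects not evaluated at Week 36 and/or Week 48 because of the hold, and it has no visit window (Protocol 7.1 and 10.11.9).

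**The concern.** A response rate tabulated at Weeks 12, 24, 36 and 48 invites reading as a persistence curve. Up to Week 36 every rating precedes any repeat-treatment, so the points are comparable. At Week 48 the retreated subjects are gone, and they left because of their Week 36 severity. The rate is then conditional on not having been retreated, and it could hold steady or rise while the effect in the whole group declines. Nothing in SAP 8.7.1 to 8.7.5 says so. The trial is described as pivotal and intended to support US approval, and these are its only effectiveness data beyond Week 36.

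**Working it through.** The documents give no Week 48 rate, no number retreated and no number on hold, so there is no stated figure to reproduce. The check traces the denominator and then illustrates the size.

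**Step 1: direction.** Let T be the Week 48 response rate in all subjects had none been retreated, r the share retreated at Week 36, and s the Week 48 rate those subjects would have had. Then

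- observed rate = (T − r·s)/(1 − r)
- bias = observed − T = r·(T − s)/(1 − r)

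The bias is zero when r = 0 and positive whenever s < T. Baseline is grade 2 or 3, the same in both folds (Protocol 9.1.1). A baseline-2 subject who meets the criterion has no one-grade improvement in either fold on that rating. A baseline-3 subject can meet it at grade 2 while still a responder. So s is expected to lie below T, but not at zero.

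**Step 2: inputs (illustrative).**

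- Durability like the comparator IFU (Protocol Appendix 22.3, product without lidocaine): 84% (57/68) at 25–36 weeks and 75% (36/48) beyond 36 weeks, taken as the Week 36 and Week 48 rates.
- Poor durability (assumed): 60% at Week 36, 45% at Week 48.
- Baseline mix 76% grade 2 and 24% grade 3 (Protocol 4.4.3, first post-marketing study).
- Assumed: a lost response is not regained; response does not depend on baseline grade; half of responders improve by two grades; latent between-fold correlation ρ of 0, 0.5 or 0.9.

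**Step 3: simulated results, no hold and all eligible subjects accept.**

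| Week 36 → 48 | ρ | r | s | Observed | Bias (points) | Retreated = non-response |
|---|---|---|---|---|---|---|
| 84% → 75% | 0 | 10.0% | 52.2% | 77.5% | +2.5 | 69.7% |
| 84% → 75% | 0.5 | 13.1% | 37.7% | 80.6% | +5.6 | 70.0% |
| 84% → 75% | 0.9 | 17.5% | 26.4% | 85.3% | +10.3 | 70.3% |
| 60% → 45% | 0 | 23.9% | 15.8% | 54.2% | +9.2 | 41.2% |
| 60% → 45% | 0.5 | 30.5% | 10.8% | 59.9% | +15.0 | 41.6% |
| 60% → 45% | 0.9 | 38.0% | 7.4% | 67.9% | +23.0 | 42.1% |

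Check of row 3 by formula: 0.175 × (0.750 − 0.264)/0.825 = 0.103.

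**Step 4: effect of the hold.** With half on hold at Week 36 and 70% acceptance, the bias falls to +0.8, +1.8 and +3.2 points (84% → 75%) and to +2.7, +4.1 and +5.8 points (60% → 45%). With all on hold at Week 36 it is 0. No scenario gave a negative value.

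**Step 5: the proposed estimate, row 1.** Eligible share: 0.76 × 0.16² + 0.24 × (0.16 + 0.42)² = 0.0195 + 0.0807 = 0.100, where 0.42 is half of 0.84. Week 36 fold response among them: 0.0807 × (0.42/0.58)/0.100 = 0.58. All-subject rate with the pre-retreatment grade carried to Week 48: 0.900 × 0.775 + 0.100 × 0.58 = 0.756. That compares with a true 0.750, an observed 0.775, and 0.697 with retreated counted as non-response.

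**Step 6: Visit 7c.** Its attendees are also not yet retreated, but many because of the hold rather than because the effect lasted. Protocol 10.11.13 ends the study at Week 48 for subjects who were not retreated unless they return for Visit 7c, so lasting responders may be absent. SAP 2.5 ends it at Visit 7c for all who do not qualify. No sign can be assigned to the bias.

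**The case against.** The strongest case against is that these are additional, descriptive endpoints. The Protocol synopsis classes them as exploratory, and no step of the testing hierarchy uses them. A rate among subjects not yet retreated is a legitimate quantity. The SAP already tabulates repeat-treatment at Week 36, Week 48, Visit 7c and never (8.1.7), so a careful reader could see the attrition. SAP 8.1.9 does not itself say observed cases; the default in 13.2.5.2 can be overridden in footnotes or in the table shells, which are not part of these documents. Retreatment removes both folds of a subject together, so the paired difference is affected less directly than the absolute rates.

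All of this stands, and it limits the consequence. It does not remove the point: the text as written leaves the denominator to the default, and the repeat-treatment table is not linked to the Week 48 rates.

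Three stronger readings are tempting and not supported:

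- *Those removed are exactly the subjects whose response was lost.* A baseline-3 fold at grade 2 is a responder and can be retreated. Subjects may decline, may meet a repeat-treatment exclusion or may have been on hold, and a subject with only one faded fold stays in.
- *Visit 7c is overstated in the same way.* Attendance depends on the hold and on who came back, so the bias could run either way.
- *The overstatement is tens of points.* Fixing 85% among those not retreated, with 60% retreated and none responding, gives 0.4 × 85% = 34%, a gap of 51 points. The documents support none of those inputs, and the largest modelled value is 23.

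**Conclusion.** The point holds for Week 48. Following the plan as written, the absolute response rates of both fillers at that visit are biased upward or at best unbiased as a measure of persistence in all treated subjects. The size is unknown. It runs from 0 (all on hold at Week 36) to about +10 points with IFU-like rates, and to about +23 with poor durability, high between-fold correlation and no hold.

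The direction rests on retreated subjects having a lower Week 48 response than those who stay. The criterion makes that likely, and the model obtains it with equal response chances for baseline grades 2 and 3; a much higher response rate in baseline-3 folds would work against it. The figures apply to NLF-SRS. For GAIS the same selection operates through its association with severity.

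For Visit 7c the finding is only that population and timing are undefined. The Week 24 primary and key secondary analyses are unaffected, as are the Week 12 and Week 36 rates.

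**What to change.** In SAP 8.7.1 to 8.7.5:

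1. Label the observed Week 48 rate as *among subjects not yet retreated*, and show beside it the numbers retreated, held, declined and missing.
2. Add a Week 48 rate on the full FAS in which a retreated subject contributes the last grade recorded before retreatment. As a sensitivity analysis, count retreated subjects as non-responders. State the rule for subjects missing Week 48 for other reasons, on which the SAP is silent.
3. Report Visit 7c separately, by actual weeks since initial treatment, and not as a further point on the response curve.
4. Reconcile Protocol 10.11.13 with SAP 2.5 on where subjects who do not qualify for repeat-treatment end the study.

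The cost is SAP wording and table programming. No new data are needed, because ratings before repeat-treatment are already scheduled (Protocol 10.11.9 and the schedule in 2.1). The downside is that an earlier grade stands in for Week 48 and may miss further fading; the non-response version bounds that from below.
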